6.1. Handling of Missing and Incomplete Data

6.1.1. Missing Dates

For the missing or partially missing dates for the adverse event, medical history, prior/concomitant medication and procedures, the missing date will be imputed following the rules below.

6.1.1.1. Adverse Events

- The missing day of onset of an AE will be set to:
 - First day of the month that the event occurred, if the onset YYYY-MM is after the YYYY-MM of first study treatment
 - The day of the first study treatment, if the onset YYYY-MM is the same as YYYY-MM of the first study treatment
 - The minimum date of the informed consent date and the first day of the month that the event occurred, if the onset YYYY-MM is before the YYYY-MM of the first treatment.
- The missing day of resolution of an AE will be set to:
 - The last day of the month of the occurrence. If the subject died in the same month, then set the imputed date as the death date.
- If the onset date of an AE is missing both the day and month, the onset date will be set to:
 - January 1 of the year of onset, if the onset year is after the year of the first study treatment
 - The date of the first treatment, if the onset year is the same as the year of the first study treatment
 - The date of informed consent, if the onset year is before the year of the first treatment
- If the resolution date of an AE or end date of an IP is missing both the day and month, the date will be set to:
 - December 31 of the year of occurrence. If the subject died in the same year, then set the imputed date as the death date.

6.1.1.2. Prior/concomitant medication/procedure

- If data indicated the stop date of a therapy is before the date of first dose, then no need to impute the start/stop date of this therapy
- The missing day for the start date of a therapy (for which a start month and year are entered) will be set to the first day of the month that the event occurred.
- The missing day for the end date of a therapy (for which an end month and year are entered) will be set to the last day of the month of the occurrence.
- If the start date of a therapy is missing both the day and month (but includes a year in which the therapy was started), the onset date will be set to January 1 of the year of onset.
- If the end date of a therapy is missing both the day and month (but includes a year in which the therapy ended), the date will be set to December 31 of the year in which the therapy ended.
- If the start date of a therapy is unknown (missing the day, month, and year) and the end date is not a complete date then the start date will be set to either the imputed partial end date or the date of the first study visit, whichever is earlier.
- If the start date of a therapy is unknown (missing the day, month, and year), the end date is a complete date, and the end date is after the date of the first study visit, then the start date will be set to the date of the first study visit. Otherwise, the start date will be set to the end date of the therapy.
- If the end date of a therapy is null and the start date is not a complete date then the end date will be set to the study end date.
- If the end date of a therapy is null and the start date is a complete date
 - and the start date is prior to the study end date then the end date will be set to the study end date.
 - otherwise, the end date will be set to the start date of the therapy.

6.1.2. Missing for Fasting Status

If fasting status is missing or incomplete, then fasting status will be considered as “not fasting.”

6.1.3. Missing for AE Relationship Status

If AE relationship status is missing or incomplete, then AE relationship status will be considered as “related.”

6.2. Analysis Visit Windows

In general, scheduled visits from randomization (except for early terminated subjects) will be used as analysis visit for descriptive analysis tables and listings. Unscheduled visits, ET visit, and EOS visit will be mapped according to the actual study day and analysis visit window defined in [Table 4](#).

Scheduled visit will be selected for analysis/summaries if has valid assessment result. If a scheduled visit is missing, the unscheduled visit that is closest to the target study day will be used for analysis purpose.

Table 4: General Analysis Visit Window

Study Period	Target Study Weeks	Target Study Day	Analysis Visit Window (Days)
Screening Period	-12 to 0	--	--
Main Study	--	1	--
	4	29	2 to 43
	8	57	44 to 71
	12	85	72 to 99
	16	113	100 to 141
	24	169	142 to min (the date all Week 24 assessments completed, Main Study cut-off date)
Extension Study	26	183	•
	30	211	(W24 End date+1) to 239
	38	267	240 to 302
	48	337	303 to 351
Follow-up Period	ET	--	--
	51/EOS	358	>= 352

Week 26 is the start visit for the extension study dosing, no need to be included in the visit-based summary tables if no data is collected.

For parameters with scheduled visit(s) at Week 12 and Week 24, or Week 24 only, the analysis window will be adjusted such that:

- The first post-baseline scheduled visit will start at day 2. Other visits start from the end of previous visit + 1 day.
- The end of each analysis visit window will be middle to the next scheduled visit (If an even number of days exists between two consecutive visits then the end date will be taken as the midpoint value minus 1 day).

6.3. Software

All data processing, summarization and analyses will be performed using SAS Version 9.4 or later of the SAS® statistical software package.

7. STATISTICAL METHODS OF ANALYSES

7.1. General Considerations

The primary analysis will include data up to the min of (28 days after the last dose date before the completion of all Week 24 assessments, the date all Week 24 assessments completed, Main Study cut-off date).

At final analysis, safety summaries including extent of exposure will report data from both Main Study and Extension Study, based on safety analysis set.

Continuous variables will be summarized by number of patients, mean, standard deviation (SD)/ standard error (SE), median, minimum, and maximum values. Minimum and maximum will be presented to the same number of decimal places as reported/collected. One additional decimal place will be presented for mean and median. Two additional decimal places will be presented for SD/ SE up to a max of three decimal places.

Categorical variables will be summarized by number and percentage of patients. Percentage will be presented to one decimal place. The number of missing values will be presented as a separate category with no percentage, but only if 1 or more patients are missing data for the summary. Otherwise, all categories will be presented (even if no patients are counted in the category). Counts of zero in any category will be presented without percentage.

For analysis purpose, placebo QW and placebo Q2W will be pooled except for exposure summaries and pre-specified supportive analyses.

All statistical tests will be 2-sided and tested at a statistically significant level of 0.05 without adjustment for multiplicity. Confidence intervals will be 2-sided 95%, unless stated otherwise. Two-sided p-values will be presented with four decimal places and values less than 0.0001 will be presented as <.0001.

Both reported units (CN) and standard units (SI) will be presented in listings. Only CN units will be used for tables and figures, unless otherwise specified. Insulin will be presented with conventional unit of μ IU/mL.

All applicable analyses for the primary analysis of the Main Study will be presented as:

<Description>	Placebo Pooled	Pegozafermin 15 mg QW	Pegozafermin 30 mg QW	Pegozafermin 44 mg Q2W
---------------	-------------------	--------------------------	--------------------------	---------------------------

A total column will be presented for the disposition, demography, protocol deviation, medical history, prior/concomitant medication/procedure, and other subject information summaries.

The listings will only present non-imputed data unless otherwise specified.

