3.6. Primary Analysis

The primary analyses will be conducted after all patients have completed the Week 24 assessments or prematurely discontinued from the study. All Main Study endpoints listed in Section 4.1 will be analyzed and reported.

The study blinding will not be broken for the study team (subjects, investigators/site personnel and Sponsor) until the final analysis. Specifically-identified sponsor personnel will be unblinded to summary results of the primary analyses for internal decision-making purpose. The list of Sponsor personnel unblinded to the summary results will be recorded in the study blinding and unblinding plan. Subjects and investigators/site personnel will remain blinded for the extension safety study.

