5.5. Treatment Emergent Adverse Event (TEAE)

TEAE during the Main Study

All AEs started or worsened within the first dose of IP up to the min of (the last dose date before the completion of all Week 24 assessments in the Main Study IP+28 days, the date all Week 24 assessments completed, Main Study cut-off date) will be considered as TEAEs during the Main Study. For subjects who withdraw consent from the Main Study, the end date of the TEAE reporting period should be the earlier of the withdrawal consent date and the date of the last dose of the IP + 28 days.

TEAE during the Study

All AEs that started or worsened on or after the first dose of study IP up to the last dose of the study IP+28 days will be considered as TEAEs.

For subjects who withdraw consent from the study, the end date of the TEAE reporting period should be the earlier of the withdrawal consent date and the date of the last dose of the IP + 28 days.

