7.8. Efficacy Analysis for Main Study

The primary efficacy endpoints are (1) proportion of subjects with NASH resolution without worsening of fibrosis at Week 24 compared to baseline (2) proportion of subjects achieving improvement of fibrosis ≥ 1 stage without worsening of NASH at Week 24 compared to baseline. The following hypothesis will be tested for each primary endpoint:

- The null hypothesis: there is no difference in the proportion of subjects meeting the primary endpoint between the placebo and each pegozafermin dose group.
- The alternative hypothesis: the proportion of subjects meeting the primary endpoint between the placebo and each pegozafermin dose group is different.

The study will be considered successful if a given pegozafermin dose group is demonstrated to be superior to the placebo group in either of the two primary endpoints at 0.05 significance level.

Estimand Framework

As detailed in the ICH E9 (R1) addendum, the following five attributes will define the estimand framework in this trial. The primary estimand will be defined as a treatment policy (TP) estimand, which compares treatment outcomes in two randomized arms at 24 weeks post-randomization irrespective of what changes in treatment could have occurred post-randomization as a result of various intercurrent events (ICE). To implement TP strategy, it will be important that outcomes are collected and recorded after occurrence of ICE's as close to the 24 week time point, regardless of what actual treatment the patient may be receiving. Below are the 5 attributes of the primary estimand:

- Treatment conditions: Randomization to Pegozafermin (15 mg QW or 30 mg QW or 44 mg Q2W) or Placebo, regardless of ICE's and deviations from the randomized treatment and actual treatment received during or at the end of the treatment period.
- Population: Randomized subjects with fibrosis stage 2 or 3 and NAS ≥ 4 at baseline per 3-panel consensus read who received at least 1 dose of IP.
- Endpoints: NASH resolution without worsening of fibrosis at Week 24 compared to baseline; improvement of fibrosis ≥ 1 stage without worsening of NASH at Week 24 compared to baseline
- Intercurrent events (ICEs): Three types of ICEs are defined below.
- Population-level summary: Between treatment group difference expressed in terms of the percentage differences in achieving the endpoints.

The following types of ICEs will be documented in course of the study.

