- ICE-1: Discontinuation of treatment due to lack of efficacy.
- ICE-2: Discontinuation of treatment due to adverse events (AE).
- ICE-3: All other events, i.e., protocol deviation, etc.

The primary analysis will use all observed outcomes at Week 24, regardless of actual treatment. All outcomes collected from patients experiencing this ICE after the actual ICE will be used in the analysis and missing values resulting from any ICE will be imputed assuming an imputation model informed by observed outcomes from similar patients with this type of ICE. The imputation model will include terms for the randomized treatment arm and the type of ICE(s) experienced by patients with missing outcomes, i.e., ICE-1,2,3 (as defined above) or None. The final inference following multiple imputation (MI) will be conducted using Rubin's combination rules.

Although the ICEs' defined above will be all handled by the same treatment policy strategy for the primary estimand, various sensitivity analyses (SA) will be conducted that will incorporate different strategies, depending on the type of ICE. For the purposes of sensitivity analysis, patients who experienced any of the listed ICEs (ICE-1,2,3), the outcomes for the primary efficacy endpoint will be considered missing starting from the occurrence of each ICE (even if outcomes are collected following an ICE) and then the missing outcomes will be imputed using appropriate imputation strategies.

For ICE-1, the SA will use the "return to baseline" hypothetical strategy, implying no benefits have been received for such patients from randomization until the end of the treatment period. The missing outcomes will be imputed using a relevant regression model fitted to the baseline data within each treatment arm with patient age, gender, baseline NAS score and stratification factors included as covariates.

For ICE-2, SA will be handled with the "control-based" hypothetical strategy implying that patients would have switched to the control treatment (i.e., placebo) starting from the occurrence of ICE-2 to the end of the treatment period. The missing outcomes will be imputed from a similar regression model fitted to the placebo arm alone with patient age, gender, baseline NAS score and stratification factors as covariates.

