In addition to the primary analysis, standard sensitivity analyses, namely, sensitivity analyses based on the hypothetical (missingness at random) strategy, return-to-baseline imputation and control-based imputation, will be conducted. The details of these analyses are presented in Table 5. In all cases, a multiple imputation approach will be applied and imputation models will be based on a Bayesian logistic regression model with subject baseline fibrosis stage, diabetes status, age, gender and baseline NAS score included in the model. The estimated effects and associated standard errors from the individual completed data sets will be combined using Rubin's rules to produce a single inferential statement (treatment effect, standard error and p-value).

Table 5: Primary and sensitivity analyses for three types of ICEs

Analysis	ICE-1	ICE-2	ICE-3
Primary analysis	Use all collected outcomes regardless of ICEs. Impute missing outcomes based on an imputation model informed by the relevant baseline data and type of ICE (“none”,1,2,3). If most subjects with ICE have missing outcomes, type of ICE covariate will be removed from the imputation model.		
Sensitivity analysis by ICE type	Set all post-baseline outcomes as missing. Impute missing outcomes based on an imputation model informed by the baseline data alone (return-to-baseline).	Set all outcomes following ICE as missing. Impute missing outcomes based on an imputation model informed by patients who did not have any of the three ICEs using only the data from the placebo arm.	Set all outcomes following ICE as missing. Impute missing outcomes based on an imputation model informed by patients who did not have any of the three ICEs using only the data from the treatment arms.

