7.8.1.1. Primary analysis

The primary analysis will be carried out using an MI-based strategy that includes the following three steps:

- Step 1. Missing outcomes will be imputed a large number of times ($M=100$) using PROC MI based on the model outlined in Table 5 based on a logistic regression model.
- Step 2. The Cochran-Mantel-Haenszel (CMH) test stratified by T2DM status (yes vs. no) and fibrosis stage (F2 vs. F3) will be applied to each completed data set to compare the proportions of responders at Week 24 between each pegozafermin group and placebo, adjusting for the stratification factors. The point estimates and associated standard errors for the differences in proportions as well as CMH test statistics will be calculated.
- Step 3. The CMH summaries from individual completed sets will be combined using Rubin’s rules to produce a single inferential statement (treatment effect, standard error, 95% confidence interval and p-value) via PROC MIANALYZE.

Note that a patient can have only one ICE (classified as ICE-1, -2, -3) or none (0). Once an ICE of specific type has occurred, the status of ICE variables remains fixed at that value until the end of the trial. All collected data are used in imputation. Imputation is done by the trial arm (TRT) but, if the data are sparse, instead of imputing by TRT, include TRT as covariate.

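### SAP 7.1 ends primary-analysis data 28 days after the last dose without exempting efficacy, which contradicts the all-observed-outcomes rule in SAP 7.8, Table 5 and 7.8.1.1

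*SAP*

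**What the plan says.** SAP 7.1 (General Considerations) sets the data limit for the Week 24 analysis: "The primary analysis will include data up to the min of (28 days after the last dose date before the completion" of the Week 24 assessments. Two further dates complete the minimum: the day those assessments are finished and the Main Study cut-off. The sentence names no data type. SAP 3.6 describes what the primary analyses contain: "All Main Study endpoints listed in Section 4.1 will be analyzed and reported". Section 4.1 includes both primary histology endpoints.

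The efficacy sections say something else.

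- SAP 7.8 defines a treatment-policy estimand that compares arms "irrespective of what changes in treatment could have occurred post-randomization as a result of various intercurrent events", and adds: "The primary analysis will use all observed outcomes at Week 24, regardless of actual treatment".
- Table 5, primary analysis row: "Use all collected outcomes regardless of ICEs".
- SAP 7.8.1.1: "All collected data are used in imputation".
- Table 4 in SAP 6.2 gives the Week 24 window as "142 to min (the date all Week 24 assessments completed, Main Study cut-off date"), with no last-dose term. For a parameter scheduled at Week 24 only, SAP 6.2 opens the window at Day 2, so an early-termination biopsy maps to Week 24.

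The Main Study adverse-event window in SAP 5.5 has the same three-part minimum as 7.1, including "the last dose date before the completion of all Week 24 assessments in the Main Study IP+28 days".

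**The concern.** A biopsy taken more than 28 days after the last dose is excluded by one section of the SAP and required by three others. If the 7.1 limit is applied when the analysis datasets are built, the efficacy rules never see that biopsy. It becomes a missing value and is imputed, although the treatment-policy estimand asks for the observed result.

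There are knock-on effects. The subject becomes a non-responder in the analysis of SAP 7.8.1.2.4 and drops out of the supportive analysis of subjects with both biopsies (SAP 7.8.1). Table 5 also removes the ICE-type covariate from the imputation model when most subjects with an ICE lack outcomes, and discarding observed post-ICE biopsies makes that more likely.

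Two programmers could therefore build different primary datasets from the same SAP. Settled after unblinding, the choice would be a data-dependent decision about which biopsies count.

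**Working it through.** **1. The plan's own figures.** SAP 3.5 assumes placebo and pegozafermin response of 15% and 45% (NASH resolution) and 20% and 50% (fibrosis improvement), with n = 64 on placebo, 64 on 30 mg QW and 40 on 44 mg Q2W, and up to 15% dropout. After dropout the sizes are 54.4, 54.4 and 34. A two-sided 0.05 test of two proportions with pooled null variance gives:

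| Comparison | NASH resolution: computed (stated) | Fibrosis: computed (stated) |
|---|---|---|
| 30 mg QW | 93.8% (94%) | 91.8% (92%) |
| 44 mg Q2W | 87.1% (87%) | 84.0% (83%) |

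The stated power is reproduced to within about 1 point, so the same rates and sizes are used in step 5.

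**2. When the 28-day term bites.** Table 4 uses Day = 7 × week + 1, so Week 24 is Day 169. The biopsy window of -7 to +14 days is Days 162 to 183. A biopsy is kept only if the last dose was on or after (biopsy day - 28):

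| Biopsy day | Earliest last dose that keeps it |
|---|---|
| 162 | Day 134 (Week 19) |
| 169 | Day 141 (Week 20) |
| 183 | Day 155 (Week 22) |

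**3. Subjects dosed to schedule.** Dosing weeks are in the schedule of activities.

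- QW, last dose before the Week 24 visit at Week 23: 162 + 28 = Day 190.
- Q2W, last dose before the Week 24 visit at Week 22: 155 + 28 = Day 183.
- Once the Week 24 dose is given: 169 + 28 = Day 197.

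All limits fall on or after Day 183, so no in-window biopsy is lost.

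**4. Who can be affected.**

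- A subject who stopped IP and whose biopsy came more than 28 days after the last dose. Protocol 7.1 asks those stopping from Week 16 to before Week 24 for a biopsy at the early-termination visit; Protocol 8.1.1 leaves other cases to consultation with the Medical Monitor.
- A subject in a temporary interruption (Protocol 7.1) lasting more than 28 days at the time of the biopsy.
- A continuing Q2W subject who skipped the Week 22 dose under Protocol 6.5.1. The last dose is then Week 20, Day 141, and the limit is Day 169. A biopsy after Day 169 and before the next dose is cut, although the subject is still on treatment.

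**5. Size per excluded biopsy.** Assume that the true off-drug response is the placebo rate and that the value is imputed at the on-drug rate. The expected shift in the estimated difference is (on-drug rate - off-drug rate)/n.

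- 30 mg QW: (45 - 15)/64 = 0.469 points, and the same for (50 - 20)/64.
- 44 mg Q2W: (45 - 15)/40 = 0.750 points, and the same for (50 - 20)/40.
- With off-drug response midway between the two rates, these halve to 0.234 and 0.375.
- If the ICE-type term stays in the model and is informative, the shift is about 0.

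Standard error of the difference = √[pa(1 - pa)/n + pp(1 - pp)/64], where pa and pp are the pegozafermin and placebo rates:

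| | NASH resolution | Fibrosis |
|---|---|---|
| 30 mg QW (n = 64) | 7.65 points | 8.00 points |
| 44 mg Q2W (n = 40) | 9.04 points | 9.35 points |

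Shift divided by standard error: 0.469/7.65 = 0.061 and 0.469/8.00 = 0.059 for 30 mg; 0.750/9.04 = 0.083 and 0.750/9.35 = 0.080 for 44 mg.

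**The case against.** The best defence is that 7.1 is general text and the primary efficacy analysis is specified separately and repeatedly. A programmer building the histology dataset would normally follow SAP 7.8 and Table 4. That is probably the intention, and the match with the adverse-event window suggests that a safety limit was carried into the general section. But the SAP states no precedence. SAP 7.1 writes exceptions where it wants them: it exempts exposure summaries from placebo pooling and confines its next sentence to safety summaries. The protocol's estimand text cannot settle the matter, because Protocol Section 9 gives the SAP precedence.

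A second defence is that the affected set may be empty. No biopsy is scheduled more than 28 days after the last dose. The early-termination visit is meant to happen when IP stops, and the later visits list only adverse events and concomitant medications. Pandemic interruptions are capped at 4 weeks plus 4 days (Protocol Appendix 6), although general interruptions under Protocol 7.1 have no stated cap. This stands as an argument about frequency and is why the point is minor. It does not remove the conflict in the text.

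A reader might infer that the cut touches only off-drug biopsies and so favours pegozafermin. Neither follows. The skipped Week 22 dose shows that a subject still on treatment can be caught. Direction depends on off-drug response, which the documents do not give, and on whether the ICE term is kept. In the missing-as-non-responder analysis, a discarded responder in an active arm moves the estimate the other way.

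**Conclusion.** The contradiction holds: SAP 7.1, read as written, excludes biopsies that SAP 7.8, Table 5 and 7.8.1.1 require. The number affected cannot be derived from the documents and is probably small, and the direction is not determined. Under the illustrative assumptions, one excluded biopsy shifts the estimate by at most about 0.47 points (30 mg QW) or 0.75 points (44 mg Q2W), or 6% to 8% of a standard error at the planned sizes.

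Three stronger readings are not supported.

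- A reader might infer a larger effect in the 15 mg arm: (45 - 15)/16 = 1.9 points per biopsy. SAP 3.5 states no power for that arm, and Protocol 4.3 expects only about a half-maximal effect there, so applying the 45% and 50% rates to it has no basis.
- A reader might take 5% to 15% of an arm as affected and obtain an overstatement of 1.5 to 4.5 points (0.05 × 30 to 0.15 × 30). No source gives such a share of subjects with an observed late biopsy; the 15% in SAP 3.5 is a dropout allowance.
- A reader might infer that the trial's conclusion is threatened. Nothing in the documents shows this.

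Severity: minor. It is a wording conflict to remove before unblinding.

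**What to change.** In SAP 7.1, apply the 28-days-after-last-dose term to safety data only. State that efficacy data include every outcome up to completion of the Week 24 assessments or the Main Study cut-off, regardless of time since the last dose, in line with SAP 7.8 and Tables 4 and 5. Make the change before the database is unblinded for the primary analysis.

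Cost: one sentence, with no new data, no new analysis and no loss of power. Optionally, add one table by arm and ICE type giving the number of subjects with observed Week 24 histology and the days from last dose to biopsy, so that a reader can see how many subjects the rule concerns.
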